 - ORR, DOR, TTR, PFS per RECIST v1.1 by Investigator
 - OS
 - Selected subgroup analysis
- Safety
 - Study drug exposure: CMP-001 and pembrolizumab
 - Prior and concomitant medications
 - Prior and concomitant procedures
 - All TEAEs (SAE, AESI)
 - Summary of clinical laboratory results
 - Summary of ECG results

H. Multiple Comparisons

No control for the effect of multiple comparisons is planned.

I. Analysis Sets

Three analysis sets will be defined for use with various analyses. The following table illustrates the relationship between each population and the analyses for which the data from the population will be used.

Regeneron Pharmaceuticals Inc. / Protocol: CMP-001-007
 IQVIA Biotech (Confidential) Project # SZA56629

Analysis Set	Analysis					
	Baseline	Subject Disposition	Efficacy	Safety	PD	Tumor Biopsy
Treated	X	X	X	X		
Pharmacodynamic					X	X
All Screened		X				

1. Treated Analysis Set

The Treated Analysis Set is defined as all subjects who receive at least 1 dose of study treatment.

2. Pharmacodynamic Analysis Set

The Pharmacodynamic Analysis Set is defined as all subjects who receive at least 1 dose of CMP-001 and have at least 1 measurable sample at Baseline and at least 1 evaluable biomarker sample after CMP-001 administration.

3. All-Screened Analysis Set

The All-Screened Analysis Set is defined as all subjects who was screened including subjects who were screen failure.

J. Subgroups of Analysis Populations

1. HPV Status

- Negative
- Positive

2. PD-L1 Expression (Combined Positive Score, CPS)

- $1 \leq \text{CPS} < 20$
- $\text{CPS} \geq 20$

3. Schedule

- A: Subjects under Schedule A are those who consented to protocol v1.0 and v2.0.
 - Per Protocol, subjects will receive CMP-001 10 mg weekly for 7 doses, after which CMP-001 will be administered every 3 weeks (Q3W), beginning on Week 10 Day 1 (W10D1), then on Week 13 Day 1 (W13D1), etc.
 - Subjects will receive Pembrolizumab 200 mg IV over 30 minutes following CMP-001 injection at Week 1 Day 1 (W1D1) and every 3 weeks thereafter (W4D1, W7D1, etc.) according to the

Regeneron Pharmaceuticals Inc. / Protocol: CMP-001-007
IQVIA Biotech (Confidential) Project # SZA56629

KEYTRUDA® (pembrolizumab) United States Prescribing Information. Pembrolizumab should be administered until the subject satisfies a condition for study treatment discontinuation.

- B: Subjects under Schedule B are those who consented to protocol v3.0, including those who reconsented to v3.0 from v2.0.

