The performance of the statistical analysis for the exploratory efficacy endpoint is contingent on the availability of the data source. Given the response assessment based on itRECIST³ by Investigator has not been collected, and that the RECIST v1.1 and iRECIST were deemed sufficient for the purpose of the response assessment in the study from the Medical's perspective, no exploratory efficacy analyses will be carried out for the exploratory phase 2 study.

IX. Safety Analyses

Safety analyses will use data from the Treated Analysis Set. Subjects will be analyzed according to the actual study treatment received.

A. Exposure

Exposure to CMP-001 and Pembrolizumab will be summarized separately for the Treated Analysis Set with descriptive statistics for the number of doses received, the average number of volumes injected per dosing visit, the duration of treatment for each treatment (weeks), the planned dose intensity, the actual dose intensity, the relative dose intensity (%), and the treatment compliance.

1. Duration of Treatment

Regeneron Pharmaceuticals Inc. / Protocol: CMP-001-007
IQVIA Biotech (Confidential) Project # SZA56629

Duration of treatment (DoT) of CMP-001 and Pembrolizumab will be summarized in a descriptive manner, respectively. DoT will be calculated as follows:

$$\text{DoT (weeks)} = [\min(\text{last dose date} + 21 \text{ days, discontinuation/completion date}) - \text{first dose date}] / 7$$

2. Dosing Intensities

(1) Actual dose intensity (mg/week) will be calculated as the total actual cumulative dose received divided by duration of treatment (weeks) for CMP-001 and Pembrolizumab, respectively.

(2) Planned dose intensity (mg/week) will be calculated as the total planned cumulative dose to be received divided by the planned duration of treatment (weeks) based on the protocol schedule.

$$\text{Planned Duration of Treatment (weeks)} = \text{number of planned treatments} \\ * 3 \text{ weeks}$$

(3) Relative dose intensity (%) will be calculated based on the actual cumulative dose received relative to the planned cumulative dose throughout the duration of treatment as follows:

$$\text{Relative dose intensity (\%)} = (\text{actual dose intensity} / \text{planned dose intensity}) * \\ 100\%$$

3. Treatment Compliance

Treatment compliance is calculated as the number of CMP-001/Pembrolizumab doses received/expected doses within the treatment period defined as time from first dose to last dose.

4. Dosage Modifications

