The number of subjects with dose modifications (e.g., Drug Delayed, Drug Withheld, Drug interrupted, Dose Reduced, Drug Permanently Withdrawn) with the reasons will also be summarized by study drug.

Additionally, subgroup analysis of drug dosing and intensities for subjects by schedule will also be performed. Listings will be provided with the information from the study drug administration eCRFs for CMP-001 and Pembrolizumab, including date and time of each dose, route of administration, dose administered, location of each injection, and the volume injected into each tumor at each dosing visit.

Regeneron Pharmaceuticals Inc. / Protocol: CMP-001-007
IQVIA Biotech (Confidential) Project # SZA56629

B. Adverse Events

Adverse events should be recorded upon first occurrence and followed until resolution. A persistent AE is continuous and does not resolve between Q3W dosing visits; and should be documented only once unless the grade becomes more severe. If the grade becomes more severe, the AE must be reported again with the new grade. Any recurrent AE should be reported as new AE each time the AE occurs. Worsening of an ongoing TEAE (i.e., an increase to higher grade) should be recorded as a new AE. Ongoing AEs that decrease in severity/grade should not be captured as new AEs.

According to Protocol section 8.1.1, disease progression, and associated hospitalizations and deaths, are not considered an AE or SAE in this study.

Medical occurrences that begin before start of study treatment should be recorded on the Medical History/Current Medical Conditions section of the eCRF, not the AE section.

Adverse events starting more than 30 days after the last dose of study treatment should not be recorded on the AE eCRF unless they are related to study treatment.

Serious adverse events and AEs resulting in discontinuation will be followed until 1 of the following occurs:

- The event resolves
- The event stabilizes
- The event returns to a Baseline value if a Baseline value is available
- The event can be attributed to agents other than the study treatment or to factors unrelated to study conduct
- The Investigator and Medical Monitor agree that follow-up is no longer necessary

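### The planned-duration formula in SAP IX.A.2 (treatments × 3 weeks) ignores CMP-001's weekly phase, so relative dose intensity is wrong for subjects dosed exactly on schedule

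*SAP*

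**What the plan says.** SAP IX.A.2 item (2) defines planned dose intensity as the "total planned cumulative dose to be received divided by the planned duration of treatment (weeks) based on the protocol schedule". The line below it sets planned duration to the "number of planned treatments" multiplied by 3 weeks. There is one version for both drugs, and a treatment is not defined.

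Item (3) describes RDI in words as based on the "actual cumulative dose received relative to the planned cumulative dose throughout the duration of treatment". It then prints RDI as actual dose intensity over planned dose intensity. Actual dose intensity is cumulative dose divided by duration of treatment (DoT).

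SAP IX.A.1 ends DoT at the minimum of the last dose date plus 21 "days, discontinuation/completion date". Planned duration has no such cut.

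SAP VI.J.3 gives two CMP-001 calendars. Schedule A is weekly for 7 doses, then every 3 weeks from W10D1. Schedule B is weekly for 2 doses, then every 3 weeks from W4D1. On membership it says: "Subjects under Schedule B are those who consented to protocol v3.0, including those who reconsented to v3.0 from v2.0". Pembrolizumab is every 3 weeks throughout.

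SAP IX.A.4 adds: "subgroup analysis of drug dosing and intensities for subjects by schedule will also be performed". Protocol 9.4 also commits to summarizing RDI.

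**The concern.** A factor of 3 weeks per treatment describes a drug given every 3 weeks. CMP-001 is not that drug during its weekly phase, so the formula departs from the protocol schedule it claims to follow. A subject who receives every planned dose on time should score 100%.

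If the formula does not return 100%, the exposure table can suggest over- or under-delivery that did not happen. It can hide missed injections, and it can show a difference between Schedules A and B that comes from the formula. The cut in DoT is a second mismatch, because it shortens one side of the ratio only.

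**Working it through.** The documents state no RDI value, so there is nothing to reproduce first.

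**Inputs.** Week of the nth dose, counted from the first:
- A: n − 1 for n ≤ 7, then 6 + 3(n − 7).
- B: 0, 1, then 3(n − 2).
- Pembrolizumab: 3(n − 1).
- DoT = week of last dose + tail, where the tail is 3 weeks or the shorter gap to discontinuation/completion.

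**Formulas.** CMP-001 is 10 mg per dose.
- Treatments = doses: planned intensity = 10n/3n = 3.33 mg/week for everyone, so RDI = (10n/DoT)/(10n/3n) = 3n/DoT.
- Treatments = 3-week visits, with k visits reached and planned dose taken up to the last dose: RDI = 3k/DoT.

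**Control.** Pembrolizumab with a full tail has DoT = 3n, so RDI = 3n/3n = 100% at every n.

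**CMP-001, on schedule up to the last dose, full 21-day tail:**

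| Last dose | DoT (weeks) | Doses: 3n/DoT | Visits: 3k/DoT |
|---|---|---|---|
| A or B, 1 | 3 | 3/3 = 100% | 3/3 = 100% |
| A, 2 | 4 | 6/4 = 150% | 3/4 = 75% |
| A, 3 | 5 | 9/5 = 180% | 3/5 = 60% |
| A, 5 | 7 | 15/7 = 214% | 6/7 = 86% |
| A, 6 | 8 | 18/8 = 225% | 6/8 = 75% |
| A, 7 | 9 | 21/9 = 233% | 9/9 = 100% |
| A, 10 | 18 | 30/18 = 167% | 18/18 = 100% |
| A, 39 (2 years) | 105 | 117/105 = 111% | 105/105 = 100% |
| B, 2 | 4 | 6/4 = 150% | 3/4 = 75% |
| B, 3 | 6 | 9/6 = 150% | 6/6 = 100% |
| B, 4 | 9 | 12/9 = 133% | 9/9 = 100% |
| B, 36 (2 years) | 105 | 108/105 = 103% | 105/105 = 100% |

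In the 2-year rows the last dose is on day 714, and 714 + 21 = 735. If completion is dated at day 730, DoT is 104.3 weeks and the dose reading gives 117/104.3 = 112% and 108/104.3 = 104%.

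**Schedule contrast.** Two subjects fully dosed to W7D1, each with DoT of 9 weeks, score 233% on A and 133% on B under the dose reading.

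**Missed doses, DoT 9 weeks.**
- A, 4 of 7 given: (40/9)/3.33 = 133% on doses; (40/9)/(70/9) = 57% on visits.
- B, 3 of 4 given: (30/9)/3.33 = 100% on doses; (30/9)/(40/9) = 75% on visits.

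**Item (3) in words.** For A with 7 doses, 70 mg is planned in the 9 weeks and 70 mg is given. That is 100%, against 233% from the printed formula on the dose reading.

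**Stopping less than 21 days after the last dose** (date read as treatment discontinuation):
- Pembrolizumab, 2 doses, stopped 7 days later: 6/4 = 150%.
- A, 7 doses, stopped 7 days later: 21/7 = 300% (doses) or 9/7 = 129% (visits).
- B, last dose W7D1, both drugs stopped at W9D1: CMP-001 12/8 = 150% (doses) or 9/8 = 113% (visits); pembrolizumab 9/8 = 113%.

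The last case can arise under the protocol. Table 1 footnote p allows the W10D1 scan up to 7 days early, and footnote a dates removal from CMP-001 to the Investigator's decision.

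**The case against.** **RDI is only descriptive.** This stands. All analyses are exploratory, there are 24 subjects, and no efficacy result or decision rule uses RDI. Dose counts, DoT, compliance, dose modifications and listings show exposure separately. They do not repair an RDI printed beside them, and the cover is partial. SAP IX.A.3 says "Treatment compliance is calculated as the number of CMP-001/Pembrolizumab doses received/expected doses within the treatment period" and ends that period at the last dose, so doses withheld after it never appear in compliance.

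**Item (3)'s words already give the right answer.** They do give 100% to a subject who missed nothing. It would be wrong to infer that nothing in the SAP points to the right figure. The words and the printed formula conflict, and the formula is what would be programmed.

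**The DoT cut does not inflate RDI for everyone.** Correct. A reader might infer a general upward bias for both drugs, but the cut acts only when the date falls less than 21 days after the last dose. That date is undefined. If it means study discontinuation, subjects who enter follow-up would rarely trigger it. On the visit reading it can also repair the shortfall: A, 3 doses, 7-day tail is 3/3 = 100% instead of 60%.

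**The 60% to 86% rows need a tail that passes the next scheduled dose.** This also stands. For A at 2, 3, 5 or 6 doses and B at 2, a full 21 days means either that the date is the study date, or that treatment was stopped late after doses had been withheld. In the second case 100% is not the right target: B with 2 of 3 due doses should read 67%, not 75%. The ends of the 103% to 233% range (B at 36, A at 7) do not depend on this.

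**Another reading might work.** A fixed 2-year plan gives 390/105 = 3.71 mg/week (A) and 360/105 = 3.43 (B). A then scores 3.33/3.71 = 90% at 1 dose and 7.78/3.71 = 209% at 7.

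**Conclusion.** The formula is wrong as written for CMP-001. On the dose reading, subjects on schedule with at least two doses and a full tail score about 103% to 233%. A and B then differ by construction, and RDI can read 100% or more with missed doses. On the visit reading, subjects whose last dose falls between visits score 60% to 86%, and the rest 100%. One dose with a full tail scores 100% on either reading.

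The tail mismatch is conditional. It raises RDI for either drug when treatment stops within 21 days of the last dose, except where it offsets the visit-reading shortfall.

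The figures ignore visit windows. The documents give no counts by schedule, so the effect on the reported summaries cannot be computed. A reader might infer that the efficacy results or the dose records are affected; nothing in the documents supports that. The matter is worth correcting before the exposure tables are produced, and it goes no further than that summary.

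**What to change.** 1. **Planned duration.** Replace the × 3 weeks rule for CMP-001 with the scheduled week of the nth dose + 3 weeks. A: n + 2 for n ≤ 7, 3(n − 4) for n ≥ 7. B: 3, 4, then 3(n − 1) for n ≥ 3. Pembrolizumab stays at 3n. Report planned dose intensity from this. For subjects reconsented from v2.0 to v3.0, use the schedule in force at each date and footnote that they sit in the Schedule B column.
2. **Count n** as doses scheduled from the first dose up to the last dose or, if doses were withheld before discontinuation, up to the discontinuation date.
3. **Tail.** Define the discontinuation/completion date as that of the study drug. For the RDI ratio only, use the same tail in actual and planned duration, and leave reported DoT and planned intensity unchanged. Where withheld trailing doses count in n, run both durations to the same end date. Footnote that RDI may then differ from the ratio of the two printed intensities. One dose stopped the same day gives DoT = 0, so state how that is shown.
4. **Item (3).** Make the words match the formula: a ratio of intensities, which delayed doses lower. With a fixed 10 mg dose, a pure cumulative-dose ratio would largely repeat compliance.

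Checks:
- A, 7 doses, stopped 7 days later: (70/7)/(70/7) = 100%.
- The missed-dose examples: 57% and 75%.
- B with dose 4 at W9D1 instead of W7D1: (40/11)/(40/9) = 82%.
- A dosed W1 to W3, two doses withheld, stopped W6D1: (30/5)/(50/5) = 60%. Counting only to the last dose would give 100%.
- B dosed W1, W2 and W4, next two withheld, stopped W13D1: (30/12)/(50/12) = 60%. Leaving actual duration at the 6-week DoT would give (30/6)/(50/12) = 120%, which is why both sides must share an end date.

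Cost: a few SAP formula and wording edits and the exposure program. No new data and no change to any dose or clinical rule.

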- ORR, DOR, and PFS based on HPV status and PD-L1 expressions (combined positive score [CPS] ≥ 1 and CPS ≥ 20)

Exploratory Endpoints:

- Response in injected and noninjected target lesions per intratumoral Response Evaluation Criteria in Solid Tumors (itRECIST) by Investigator assessment
- Baseline, and change from Baseline, in tumor or blood measurements of biomarkers related to TLR9, immune checkpoints, and potential markers of resistance or response to immunotherapy
- Change from Baseline in blood concentrations of C-X-C motif chemokine 10 (CXCL10) (IP-10) and other cytokines after treatment with CMP-001
- Blood concentrations of CMP-001 or its metabolites

Methodology:

This is a multicenter, open-label, Phase 2 clinical trial of CMP-001 administered by IT injection in combination with intravenous (IV) pembrolizumab in subjects with recurrent or metastatic head and neck squamous cell carcinoma (HNSCC) not previously treated with a PD-1 blocking antibody. This will be a Phase 2 study, with response and DOR assessments using RECIST v1.1 and iRECIST criteria according to Investigator assessment. All subjects will receive CMP-001 IT and pembrolizumab IV according to the treatment schedule until a reason for treatment discontinuation is reached.

Number of subjects (planned):

A total of 43 subjects is planned for this study. This is based on the following assumptions:

- A historical ORR of 19% with pembrolizumab monotherapy in subjects with HNSCC who have a CPS ≥ 1 and were not previously treated with a PD-1 blocking antibody (null hypothesis)
- An anticipated ORR of 35% with CMP-001 and pembrolizumab (alternative hypothesis).
- Power of 80% and one-sided alpha level of 0.05.

Diagnosis and main criteria for inclusion:**Inclusion criteria:**

Subjects enrolled in the study must meet all of the following inclusion criteria to be eligible:

1. Subjects with histologically- or cytologically-confirmed recurrent or metastatic HNSCC considered incurable by local therapies, and subjects with T4 or N3 disease who are ineligible for or refusing local therapies.
2. No prior systemic therapy in the recurrent or metastatic setting. Systemic therapy as part of multi-modal treatment for locally advanced disease is allowed.
3. Primary tumor locations of oropharynx, oral cavity, hypopharynx, larynx, paranasal sinus, or HNSCC of unknown primary origin. Participants may not have a primary tumor site of nasopharynx (any histology).

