Stop dates of AEs / Concomitant Medications will be imputed as follows:

- Completely missing stop date will not be imputed.
- Stop date missing both the month and day will be imputed as Dec 31st of the year of stop date.
- Stop date missing the day will be imputed as the last date of the month of the stop date.
- After imputation, the imputed date will be compared against the date of death, if available. If the planned imputed date is later than the date of death, the date of death will be used as the imputed date instead. If there is no date of death in the EDC for a subject and the planned imputed date is later than the End-of-Treatment (the last drug received) date + 30 days, then the End-of-Treatment (EOT of the last study drug received) date + 30 days will be used for the stop date.

Missing Dates in Prior Medications

Start or Stop dates of Prior Medications will be imputed as follows:

- Completely missing start or stop date will not be imputed.
- Start or stop date with missing both the month and day will be imputed as Dec 31st of the year of stop date.
- Start date missing the day will be imputed as the 1st of the month of the start date.
- Stop date missing the day will be imputed as the last date of the month of the stop date or the study first dose date, whichever comes earlier.

D. Multiple Study Centers

No adjustment for study center is planned.

E. Covariate Adjustment in Primary Analysis

No covariate adjustments are planned.

F. Sample Size Reassessment

Not applicable.

Regeneron Pharmaceuticals Inc. / Protocol: CMP-001-007
IQVIA Biotech (Confidential) Project # SZA56629

G. Ad-hoc Analyses

There will be an ad-hoc analysis planned with the trigger event being two disease assessments after the enrollment of the last subject. The ad-hoc analysis of the endpoints will follow the efficacy analysis methods described in Section **Error! Reference source not found.** below as well as the safety analysis methods detailed in Section **Error! Reference source not found.** below for the exploratory Phase 2 study.

The following unblinded subject information, efficacy-related and safety-related data displays will be produced for the purpose of the ad-hoc analysis. Unless stated otherwise, these displays are summary tables that summarize data for the corresponding analysis set:

- Subject information
 - Demographics
 - Baseline characteristics
 - Disposition
 - Medical history
 - Cancer history
 - ECOG
- Efficacy

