- Subjects with pembrolizumab-related TEAEs
- Subjects with grade 3 or higher TEAEs Related to CMP-001 and/or Pembrolizumab
- Subjects with grade 3 or higher CMP-001-related TEAEs
- Subjects with grade 3 or higher pembrolizumab-related TEAEs
- Subjects with treatment-emergent Serious AEs (SAEs)
- Subjects with SAE Related to CMP-001 and/or Pembrolizumab
- Subjects with CMP-001-related SAEs
- Subjects with pembrolizumab-related SAEs
- Subjects with AE of Special Interest

Regeneron Pharmaceuticals Inc. / Protocol: CMP-001-007
IQVIA Biotech (Confidential) Project # SZA56629

- Subjects with TEAEs leading to CMP-001 and/or Pembrolizumab Treatment Discontinuation
- Subjects with TEAEs leading to CMP-001 treatment discontinuation
- Subjects with TEAEs leading to Pembrolizumab Treatment Discontinuation
- Subjects with TEAEs leading to study discontinuation
- Subjects with TEAEs resulting in death

In addition, the following TEAE summaries tables will be generated. Percentages will be based upon the number of subjects in the Treated Analysis Set.

- All TEAEs, by MedDRA SOC and preferred term
- Grade 3 or higher TEAEs, by MedDRA SOC and preferred term
- TEAEs by maximum severity, by MedDRA SOC and preferred term
- TEAEs Related CMP-001 and/or pembrolizumab by maximum severity, by MedDRA SOC and preferred term
- TEAEs Related CMP-001 by maximum severity, by MedDRA SOC and preferred term
- TEAEs Related Pembrolizumab by maximum severity, by MedDRA SOC and preferred term TEAEs by highest relationship to CMP-001 and/or Pembrolizumab, by MedDRA SOC and preferred term
- Grade 3 or higher TEAEs Related to CMP-001 and/or pembrolizumab by MedDRA SOC and preferred term
- Grade 3 or higher CMP-001-related TEAEs, by MedDRA SOC and preferred term
- Grade 3 or higher pembrolizumab-related TEAEs, by MedDRA SOC and preferred term
- Death due to TEAEs, by MedDRA SOC and preferred term
- Serious AEs (SAEs), by MedDRA SOC and preferred term
- Grade 3 or higher SAEs, by MedDRA SOC and preferred term
- Grade 3 or higher CMP-001-related SAEs, by MedDRA SOC and preferred term
- Grade 3 or higher pembrolizumab-related SAEs, by MedDRA SOC and preferred term
- SAEs related to treatment (possibly + probably + definitely), by MedDRA SOC and preferred term
- SAEs related to CMP-001 by MedDRA SOC and preferred term
- SAEs related to pembrolizumab by MedDRA SOC and preferred term
- TEAEs leading to CMP-001 and/or Pembrolizumab treatment discontinuation

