Regeneron Pharmaceuticals Inc. / Protocol: CMP-001-007
IQVIA Biotech (Confidential) Project # SZA56629

- TEAEs leading to CMP-001 treatment discontinuation
- TEAEs leading to pembrolizumab treatment discontinuation
- TEAEs leading to study discontinuation by SOC and preferred term

Additionally, subgroup analysis for the overall summary of adverse events by schedule will also be performed. A by-subject AE data listing, including verbatim term, SOC, preferred term, severity, outcome, and relationship to treatment, will be provided. Listed terms will be ordered alphabetically within subject. Separate listings will be generated for deaths, SAEs and AEs leading to treatment and study discontinuation.

C. Deaths

All deaths that occur during the study or within the protocol-specified follow-up period after the last dose of the study drug will be reported.

Death information to be included in the summary table concerns the incidence of deaths, along with the primary cause of death for the Treated Analysis Set. All deaths including deaths that occur within 30 days after the last dose of the study treatment or the initiation of an alternative new anti-cancer therapy, whichever is earlier, will be tabulated and presented in a by-subject listing, involving the primary cause of death, duration of treatment and the number of days between the last dose date of the study drug and death. Additionally, subgroup analysis for deaths by schedule will also be performed.

D. Clinical Laboratory Results

Gradable laboratory values will be evaluated and assigned toxicity grades according to the NCI CTCAE v5.0. Clinically significant post-baseline laboratory values will be reported as AEs. When possible, a diagnosis should be recorded as an AE, rather than the symptoms or isolated laboratory abnormalities related to the diagnosis.

Safety central laboratory data, including hematology, coagulation, serum chemistry, autoimmune lab panel and thyroid function tests (see Table 3 below), will be summarized using descriptive statistics (mean, standard deviation, median, minimum, and maximum) and presented for each time point, including change from Baseline, for the Treated Analysis Set. Shift tables from Baseline to the Min and Max Post-Baseline, the categories in the shift tables will be WNL, Low, and High. Within normal limits and Normal will be used when appropriate for urinalysis parameters.

Regeneron Pharmaceuticals Inc. / Protocol: CMP-001-007

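### Deaths and the AE overview by schedule are crude percentages of subjects, although the protocol dates imply longer potential follow-up for Schedule A than for subjects newly consented to Schedule B

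*SAP*

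**What the plan says.** SAP IX.C tabulates the incidence of deaths and their primary cause in the Treated Analysis Set, then says: "Additionally, subgroup analysis for deaths by schedule will also be performed". SAP IX.B sets out a TEAE overview as number and percent of subjects and adds: "subgroup analysis for the overall summary of adverse events by schedule will also be performed". SAP VI.K takes the number of subjects in the corresponding analysis population as the default denominator. A further sentence in IX.B, "Percentages will be based upon the number of subjects in the Treated Analysis Set", introduces the system organ class and preferred term tables rather than the overview. Neither section provides person-time, a common time window or a summary of follow-up.

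Schedule is defined in SAP VI.J.3: "Subjects under Schedule A are those who consented to protocol v1.0 and v2.0". Schedule B is consent to v3.0, including subjects re-consented from v2.0. SAP I.B dates the three protocol versions 11 June 2020, 3 August 2021 and 14 January 2022. SAP II.C dates the last enrolment 22 June 2022 and gives 24 treated subjects, without first-dose dates or a split by schedule.

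On timing, SAP VI.G says: "There will be an ad-hoc analysis planned with the trigger event being two disease assessments after the enrollment of the last subject". Its display list has OS, selected subgroup analyses and TEAEs. It names no deaths table, although it refers generally to the SAP's safety methods. SAP VIII.C plans OS by Kaplan-Meier and repeats it by schedule.

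**The concern.** The schedules are largely consecutive cohorts. On any cut date a subject who started under v1.0 or v2.0 has had more calendar time in which to die than one who joined under v3.0. A percentage of subjects treats these unequal times as equal, so A would be expected to show more deaths even if the schedules had the same survival.

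The direction makes this awkward. Schedule A is the denser one (seven weekly CMP-001 doses against two), so the artefact points the same way as a real schedule-related toxicity signal and could be read as one. It could also leave a safety table at odds with the censored OS result in the same report.

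**Working it through.** **Plan figure.** The documents state no death percentage by schedule, so there is none to reproduce. The one design calculation (43 subjects, ORR 19% against 35%, one-sided 0.05, 80% power) comes out at 42.8, rounded up to 43, but plays no part here.

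**Cut date.** Scans fall at W10D1 and W19D1 (SAP VIII). W19D1 is 18 × 7 = 126 days after first dose; 22 June 2022 + 126 days = 26 October 2022.

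**Potential follow-up at that cut** (days / 30.4375):
- from 11 June 2020: 867 days, 28.48 months
- from 3 August 2021: 449 days, 14.75 months
- from 14 January 2022: 285 days, 9.36 months
- from 22 June 2022: 126 days, 4.14 months

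Newly consented B subjects therefore have 4.14 to 9.36 months. For A, two assumed entry periods end on 14 January 2022: one starts on 3 August 2021 (9.36 to 14.75 months), the other on 11 June 2020 (9.36 to 28.48 months).

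**Formula.** Same exponential survival in both schedules, λ = ln 2 / median, entry uniform so that follow-up is uniform on [a, b]:

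P(death by cut) = 1 − (e^(−λa) − e^(−λb)) / (λ(b − a))

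For the 14.9-month median that protocol section 1.1 cites for pembrolizumab monotherapy, λ = 0.0465:
- B: 1 − (0.825 − 0.647)/0.243 = 26.8%
- A from August 2021: 1 − (0.647 − 0.503)/0.251 = 42.8%
- A from June 2020: 1 − (0.647 − 0.266)/0.889 = 57.2%

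| Median OS (months) | B % | A % from Aug 2021 | A % from Jun 2020 | A/B |
|---|---|---|---|---|
| 10 | 37.0 | 56.4 | 71.1 | 1.52 to 1.92 |
| 10.7 | 35.1 | 54.0 | 68.7 | 1.54 to 1.96 |
| 13 | 30.0 | 47.2 | 61.9 | 1.57 to 2.06 |
| 14.9 | 26.8 | 42.8 | 57.2 | 1.60 to 2.13 |
| 20 | 20.8 | 34.1 | 47.2 | 1.64 to 2.27 |

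The medians 10.7, 13 and 14.9 are cited in protocol section 1.1; 10 and 20 widen the range.

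**Later site switch.** If sites moved to v3.0 on 15 March 2022 instead, the ratio is 1.63 to 2.34 over medians 10.7 to 14.9.

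**Re-consent.** A simulation moved every v2.0 subject still on treatment on 14 January 2022 into B (assumed median time on treatment 3 or 6 months). The ratio is 1.62 to 2.06 over medians 10.7 to 14.9. B gains longer-followed subjects, but only ones who survived on treatment to re-consent.

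**Study end.** SAP II.F ends the study 30 days after the last dose of the last ongoing subject. Taking 2 years from 22 June 2022 plus 30 days gives 22 July 2024. Expected deaths are then 72 to 83% in B and 78 to 92% in A over medians 10.7 to 14.9, a ratio of 1.06 to 1.16 (1.05 to 1.21 over 10 to 20). An earlier end would give a ratio between this and the October 2022 one.

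**AE overview.** TEAEs are limited to first dose until 30 days after last dose, and AE collection stops at new cancer treatment (SAP IX.B). The simulation used the 30-day limit, first-event rates of 0.05 to 0.3 per month and median treatment of 3 or 6 months (all assumed). The October 2022 ratio is about 1.04 to 1.4.

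**Chance.** With 10 to 16 of the 24 subjects in A, a 13-month median and A entry from January 2021, the 10th to 90th percentile of the observed death ratio is about 1.0 to between 4 and 5.

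**After adjustment.** With identical survival the rate is the same in both schedules: 100 × 0.693/13 = 5.3 deaths per 100 person-months at a 13-month median (6.5 at 10.7, 4.7 at 14.9), and 6-month survival is about 73% in both.

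**The case against.** The strongest reply is that the deaths are already analysed properly: OS by schedule uses Kaplan-Meier, which censors for unequal follow-up. Dosing and disposition by schedule are planned too, and the death listing gives treatment duration and days from last dose to death. This stands. It limits the point to a crude table beside a censored one, and it would be wrong to call these tables the only information on the two schedules. Kaplan-Meier does not correct the cause-of-death table or the AE rows, however. Run from first dose, it also does not remove the survivor effect of counting re-consented subjects in B.

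Second, a deaths table is not named for the ad-hoc analysis, and by study end the distortion is small. This stands as well; the larger ratio applies only if the table is produced at the earlier cut.

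Third, there are 24 subjects, everything is descriptive, and chance is larger than the artefact. That lowers the priority. It does not justify a display with a known directional bias that a few columns remove.

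Four stronger readings are tempting, and the documents do not support them:
- A reader might put the ratio as high as 2.5. On these dates that needs every A subject to have entered before 3 August 2021, which leaves no v2.0 entrants in A, although SAP VI.J.3 puts v2.0 consents there.
- A reader might carry the death ratio over to the AE overview. The TEAE window rules that out.
- A reader might dismiss any AE excess in A as artefact. The schedules differ in early dosing, so a real effect is possible.
- A reader might take longer observation of A as established. It is inferred from version dates; actual entry dates and the split are not given.

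**Conclusion.** The point holds in limited form. The by-schedule deaths table and AE overview make no allowance for observation time, and the version dates imply longer potential follow-up in Schedule A than in newly consented Schedule B. If the all-deaths table is produced at an October 2022 cut, the expected ratio under identical survival is about 1.5 to 2.3; at the 14.9-month median the gap is 16 to 30 percentage points (42.8 − 26.8 and 57.2 − 26.8). At study end the ratio is about 1.06 to 1.16. For the AE overview the effect is smaller, about 1.04 to 1.4 on assumed event rates.

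These are expected values. They rest on exponential survival, uniform entry and assumed entry periods for each schedule. Adjusting the tables is worth doing, but it does not affect the primary analysis.

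**What to change.** In SAP IX.C, add to the by-schedule deaths table total person-months of follow-up, deaths per 100 person-months, and the planned Kaplan-Meier survival estimates at fixed times. At an October 2022 cut those times must lie within B's follow-up; 6 months does, but 12 and 18 months exceed the 9.4-month maximum for newly consented subjects. In SAP IX.B, add to the by-schedule overview the person-months of TEAE observation (first dose to 30 days after last dose or new cancer treatment) and exposure-adjusted rates. Keep the crude figures and name the schedule subgroup N as their denominator.

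For v2.0 subjects re-consented to v3.0, assign person-time and events before re-consent to Schedule A and after it to Schedule B, or show these subjects in a separate column.

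A fixed early window, such as the first 18 weeks, should be supplementary at most and should exclude re-consented subjects. Otherwise it credits TEAEs from their Schedule A period to B, and anyone re-consenting after week 18 contributes no window deaths to B by construction.

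The cost is a few columns. With 24 subjects the rates will be imprecise, and a rate per person-month summarises well only if the hazard is roughly constant, which is why the fixed-time estimates should stand beside it.
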